10.1 Missed Follow-Up

If the patient cannot be reached for a follow up visit at least three telephone contacts (or attempts) should be made then a courier with the questionnaire should be sent to the patient prior to recording a missed follow-up visit. The patient however remains in the study until the 1 year follow-up. The patient will only be considered as 'Lost to follow-up' if he/she cannot be reached for the final 2 years follow-up.

10.2 Patient withdrawal

Every effort will be made by the investigator to keep the patient in the study; however should the patient decide to withdraw, the investigator is responsible for reporting the observations thoroughly, and completing the final evaluations and eCRFs.

10.3 Data Collection from withdrawn/ discontinued patients

In patients who withdraw their consent before the randomization has occurred no data collection will be carried out. These patients are considered screen failures and will be documented as such on the Subject Screening and Eligibility Log.

For patients who were declared eligible for the study and randomized but who are discontinued for any reason prior to the commencement of any PCI procedure, data until that time period will be collected and the patient will be immediately withdrawn from study. The reason for the early withdrawal must be documented in the case report form.

For patients who withdraw their consent after the commencement of any PCI procedure, a final study visit will be conducted. Data will be collected on the eCRF.

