Primary analytical population	The primary analysis of the composite endpoint of all-cause mortality, myocardial infarction, stroke and ischemia-driven target lesion revascularization will be performed on the intent-to-treat (ITT) population.
Statistical Method	The primary endpoint is a composite of all-cause mortality, myocardial infarction, stroke or ischemia-driven TLR with an

	
anticipated median follow-up of one year (efficacy).
 
The SENIOR study is powered to test the superiority of the Synergy[®] II with a relative 25% reduction of the primary endpoint
 
Assuming the following:
 
• primary endpoint event rate is 31% in control treatment arm at 1 year (interpolated from the most contemporary and accurate references)• minimum time to follow-up is 1 year• a constant dropout rate yielding 15% lost to follow-up at 1 year• two-sided alpha = 0.05• then a sample size population of 560 subjects per arm will provide 80% power to demonstrate superiority using a chi-square test comparing the event rates at 1 year from the Kaplan-Meier curves. The definitive total number will be 1.200 patients (600 in each arm).
--	--

1-Introduction

Coronary artery disease is a prevalent disease in patients ≥ 75 years with or without other risk factors. Aging of the population leads to frequent hospitalizations and significant medical and economic burden. However, there is currently no clear recommendation for how to treat specifically patients above 75 years suffering coronary artery disease (CAD). Patients above 75 years of age have been systematically underrepresented and highly selected in major clinical randomized trials underlying current recommendations for general population suffering stable or unstable CAD (1).

2-Background

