6.3. Informed Consent

Prior to participation in the study, all eligible subjects must review, date and sign the Study Patient Informed Consent (PIC) form.

Eligible patients may only be included in the study after providing written (witnessed, where required by law or regulation), EC approved informed consent, or, if incapable, and if required by local law or regulation, after such consent has been provided by a legally acceptable representative of the patient. In the case of witnessed verbal consent, written informed consent should be obtained within 24 hours of procedure and must be obtained before discharge. Failure to obtain signed informed consent renders the patient ineligible for the study.

According to the European Directive 2001/20/EC of 4 April 2001, in emergency cases, a consent must be given by a patient's legal representative (if present); if the person concerned is unable to write, oral consent in the presence of at least one witness may be given in exceptional cases, as provided in national legislation. In this study, any verbal consent given by a patient in an emergency situation will be witnessed and documented. Written consent will be obtained as soon as the patient is able to provide written consent.

Any changes to the proposed consent form must be agreed to by the sponsor before

submission to the EC and a copy of the approved version must be provided to the CERC after EC approval.

The Investigator or designated member of the study site personnel must explain the study in detail, talking through all details described in the PIC. The patient must be given the opportunity to ask questions and ample time to consider his/her participation. If the patient is willing to participate in the study he/she or legal representative must sign and date two copies of the Informed Consent, which must be signed and dated at the same time, by the investigator or designee who explained the study. One copy of the PIC will be given to the patient and the other one will be retained in the study specific binder at the site. The process of obtaining informed consent should be documented in the patient source documents.

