Antithrombotic regimen within the cathlab, including unfractionated heparin, low molecular weight heparin, bivalirudin, fondaparinux, is left to the physician discretion. GpIIb / IIIa inhibitors can be used in selected cases in patients with STEMI but are not recommended for stable patients or for patients with silent ischemia.

-Dual antiplatelet therapy will be administered for **similar duration** after Synergy[®] II and Omega[®]/Rebel[®] stent or any other BMS available implantation. DAPT duration will be one month after PCI for stable angina and silent ischemia, and six months after PCI for acute coronary syndroms, **irrespective of the type of stent** (Synergy[®] II or Omega[®]/Rebel[®] stent).

-Aspirin will be prescribed to all patients at an initial intra venous or oral loading dose of 150-300mg and at a maintenance dose of 75-100 mg orally daily, indefinitely (except in patients with chronic anticoagulation). For patients not already on P2Y₁₂ inhibitors they will be added to aspirin before or immediately after percutaneous coronary intervention and maintained over one month (stable angina or silent ischemia) or 6 months (ACS).

-All patients in the trial will be treated by either:

-clopidogrel 600mg loading dose and 150mg/d or 75mg/d

OR

-prasugrel 60mg loading dose and 5 mg/d orally

OR

-ticagrelor 180mg loading dose and 90mg/bd orally

over one month after PCI. The P2Y₁₂ inhibitor will be prolonged over 6 months only in patients with acute coronary syndrome, irrespective of the type of the stent.

Optimal medical treatment.

Anti ischemic treatment should be added to medical treatment and include beta blocker agents in patients without contra indication.

Calcium channel blocking agents can replace beta blocker agents in patients with contra indications to these agents.

A proton pump inhibitor (PPI) is strongly recommended according to physician discretion (pantaprazole 20mg, ezoprazol 20mg, lanzoprazole 20mg, rabeprazole 20mg or omeprazole 20mg).

10-Follow-up visits

Every effort should be made for collecting the subject data thanks to an on-site visit or telephone contact, as described below:

- 30 days(+/- 5 days) visit: office visit

-
- 180 (+/-2 weeks): telephone contact or office visit
 - 1 year visit (+ 4 weeks): office visit
 - 2 years (+/-4 weeks) visit: telephone contact or office visit.

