10.4 Data Collection for patients who receive non-study stents

Patients who receive non-study stents or who undergo any non-study procedure for the treatment of coronary artery disease (i.e. any procedure that is not PCI with a study stent) for any reason, are considered major protocol violations and will be followed for the intent to treat (ITT) analysis only. Patient care (i.e. medical treatment, additional procedures) is left to the discretion of the investigator, however, patients must continue to be followed per protocol scheduled follow-up.

11- Study discontinuation rules

If the Sponsor, Data Safety and Monitoring Board, Regulatory Agency, and/or the Principal Investigator discover conditions during the study that indicate the investigation should be terminated for patient safety reasons, an appropriate schedule for termination will be setup.

12-Statistical design and analysis

The trial is designed to be a superiority trial. This is a randomized, controlled, single blind, multicentric, prospective trial. The primary endpoint is a composite of all-cause mortality, myocardial infarction, stroke or ischemia-driven TLR with an anticipated median follow-up of one year (**efficacy**).

The SENIOR study is powered to test the superiority of the EESbp with a relative 25% reduction in the active group.

Assuming the following:

- primary endpoint event rate is 31% in control treatment arm at 1 year (interpolated from the most contemporary and accurate reference)
- minimum time to follow-up is 1 year
- a constant dropout rate yielding 15% lost to follow-up at 1 year
- one-sided alpha = 0.025

then a sample size population of 560 subjects per arm will provide 80% power to demonstrate superiority using a chi-square test comparing the event rates at 1 year from the Kaplan-Meier curves. To take into account potential patients loss during follow up, the definitive total number will be **1,200 patients** (600 in each arm). The sample size calculation was performed in SAS version 9.2 using 10.000 simulations.

All statistical analyses will be described in a statistical analysis plan, which will be finalized before the end of the study.

13-Safety reporting

Safety of the subjects participating in this clinical trial will be monitored throughout the trial using the Adverse Event reporting process to identify real and potential safety issues.

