13.2 Safety reporting

All endpoints related events, serious or not, that occur to any subject implemented with Synergy[®] II or Omega[®]/Rebel[®] stent, regardless of attribution, that are identified for any subject from PCI till the 12 month follow-up visit will be collected in the eCRF.

All serious endpoints related events irrespective of potential causal relationship to the study must be reported to the CERC within 24 hours of the Investigator's first knowledge of the event. All serious endpoints related events must be followed up for outcome of the event. Follow-up information of the serious endpoints related events should be provided by the investigator within the same reporting period (i.e. within 24 hours of identification)

14- Scientific Committee (SC)

The SC will be responsible for maintaining the scientific integrity of the trial and will monitor the progress of the trial. The SC will approve the trial protocol and any subsequent amendments and the case record forms. The SC will meet prior to the start of the trial and as required during the trial progress.

15- Data Safety Monitoring Board (DSMB)

An independent DSMB will be established. The DSMB will consist of cardiologist, neurologist, statistician and clinician with experience of clinical trials. Their main role is to consider the data from any event analysis and specifically to assess any safety issues such as unexpected adverse events that occur and report back to the SC and CEC. The DSMB will develop a charter outlining their responsibilities and operational details.

16- Clinical Events Committee (CEC)

A clinical events committee (CEC) will be established to review the details of key trial adverse endpoint related events. Their reports will be used in the assessment of endpoints and for presentation of data to the DSMB.

17- General study conduct

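### Section 10.3 ends data collection on randomised patients who never start PCI, against the ITT primary analysis and section 4-2, and section 13.2 words event collection too narrowly

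*Protocol*

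**What the plan says.** Section 8 places randomisation before PCI. Under section 6.4.4 a patient counts as enrolled once consented, randomised and given an assignment, with a lesion treatable by a study stent. The Protocol Summary states that the primary analysis "will be performed on the intent-to-treat (ITT) population".

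Five provisions then say whose outcomes are collected:

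- **Section 4-2** follows all randomised subjects for at least one year, counted from the baseline procedure.
- **Section 10** collects MACCEs and bleeding at the scheduled visits, with no restriction by stent received.
- **Section 10.3** covers patients who were "randomized but who are discontinued for any reason prior to the commencement of any PCI procedure". For them, "data until that time period will be collected and the patient will be immediately withdrawn from study".
- **Section 10.4** covers patients given a non-study stent or any non-study procedure. They "are considered major protocol violations and will be followed for the intent to treat (ITT) analysis only", on the protocol visit schedule.
- **Section 13.2** describes collection in the eCRF of "All endpoints related events, serious or not, that occur to any subject implemented with Synergy[®] II or Omega[®]/Rebel[®] stent", in a window running from PCI to the 12-month visit.

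**The concern.** An ITT analysis needs outcomes on everyone randomised. Section 10.3 tells sites to stop collecting them for one group, and its trigger is any reason for discontinuation, not only withdrawal of consent. A patient who becomes unstable after randomisation, or whose operator reconsiders PCI, could be removed on the day of randomisation.

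The trial is single blind, and the operator has to know which stent is assigned in order to implant it. The decision not to start PCI can therefore be taken with the allocation known, and it may be related to prognosis. If it is related to both, the arms compared at one year are no longer the arms that were randomised. A later analysis plan can define the ITT set, but it cannot supply outcomes that sites were told not to collect.

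**Working it through.** **Setting the sections side by side**

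1. Patient randomised, no procedure started. Section 4-2: follow for at least one year. Section 10.3: withdraw at once. These are incompatible. Section 4-2 also counts time from a baseline procedure that this patient never has.
2. Patient randomised, then sent to a non-PCI procedure before PCI starts. Section 10.3: withdraw. Section 10.4: keep and follow for ITT. Both rules apply, and sites could use either.
3. Patient given a non-study stent. Sections 10 and 10.4: follow and collect MACCEs. Section 13.2: outside its wording. These conflict.
4. Event between randomisation and PCI. Section 13.2: outside its window, although the patient is already enrolled.

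**The plan's own figures**

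Inputs from section 12: control rate 31%, relative reduction 25%, dropout 15% at one year, one-sided alpha 0.025, 560 per arm, 80% power, comparison of one-year Kaplan-Meier rates.

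- Active rate: 0.31 × 0.75 = 0.2325. Planned difference: 31 − 23.25 = 7.75 points.
- With exponential event and dropout times, λ = −ln(1 − p) and γ = −ln(0.85), the Greenwood variance of the one-year rate is (1 − p)² · λ/(λ + γ) · (e^(λ+γ) − 1)/n.
- At n = 560 the standard error of the difference is √((0.2334 + 0.1945)/560) = 2.76 points. Then 7.75/2.76 = 2.80, and power is Φ(2.80 − 1.96) ≈ 80.1% (80.6% in 10,000 simulations).

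The stated 80% reproduces, so the planning figures can be taken as they stand.

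**How far withdrawal could move an arm's rate**

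The documents give no rate of discontinuation before PCI, so the following is an assumed range. A patient withdrawn before PCI is censored at about time zero and so drops out of the Kaplan-Meier estimate. Let a share w of one arm be withdrawn, with true event rate q, and let the whole arm's rate be p. Then

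observed rate = (p − wq)/(1 − w), and shift = −w(q − p)/(1 − w).

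Control arm only, p = 31%, shift in percentage points:

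| w (patients of 600) | q = 31% | q = 50% | q = 60% |
|---|---|---|---|
| 1% (6) | 0 | −0.19 | −0.29 |
| 2% (12) | 0 | −0.39 | −0.59 |
| 3% (18) | 0 | −0.59 | −0.90 |
| 5% (30) | 0 | −1.00 | −1.53 |

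Example: (0.31 − 0.05 × 0.60)/0.95 = 0.2947, a fall of 1.53 points.

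The same formula for the Synergy arm only, p = 23.25%, runs from −0.01 × 0.2675/0.99 = −0.27 points (w = 1%, q = 50%) to −0.05 × 0.3675/0.95 = −1.93 points (w = 5%, q = 60%).

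The direction depends on the arm. Losing high-risk control patients narrows the observed difference; losing high-risk Synergy patients widens it. Losing patients at lower risk than their arm reverses each effect.

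**The case against.** The strongest reply is that the protocol, read as a whole, protects ITT. Sections 4-2, 10 and 10.4 keep non-study-stent and non-study-procedure patients under scheduled follow-up with MACCE collection. Section 13.2 is a safety-reporting section whose window stops at 12 months although section 5-2 sets two-year endpoints, so it cannot be the only rule for endpoint capture. The ITT definition and time zero may properly be left to the analysis plan.

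Most of this stands, and it rules out several stronger readings:

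- A reader might infer from 13.2 that events are collected only in study-stent recipients. The documents do not support that: 13.2 is a narrower, contradictory wording, not a bar.
- A reader might infer that failed stent delivery or later conversion to bypass surgery removes a patient. These arise after PCI has begun or are non-study procedures, so 10.4 retains the patient. Only diversion before PCI starts falls in the overlap.
- A reader might take "stent or any other BMS available implantation" in section 9.2 as a leak confined to the control arm. The phrase sits in a sentence on the duration of antiplatelet therapy; section 4-3 requires the assigned stent, and 10.4 keeps any patient given another one.
- Section 6.3 says "Failure to obtain signed informed consent renders the patient ineligible for the study". That a patient randomised on verbal consent who dies before signing leaves the ITT set is an inference; the text does not say so.
- A reader might compute a large loss of power. That requires counting the missing patients as event-free, largely in a group that 10.4 retains, and ignoring the planned Kaplan-Meier censoring and the 15% dropout. The documents do not support such a figure.

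What the reply does not answer is section 10.3 itself. No other section restores follow-up for a patient discontinued before any procedure begins.

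**Conclusion.** The point holds in limited form. Section 10.3 contradicts the ITT primary analysis and section 4-2 for randomised patients who do not start PCI, and it overlaps with 10.4. Section 13.2 is worded more narrowly than 10.4 and section 10, and its window leaves out the interval between randomisation and PCI.

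The consequence is exposure to bias. A reader might go further and say that the ITT analysis cannot be done without bias, but that depends on how many patients are withdrawn, in which arm and at what risk, and the documents give none of these. Under the assumed 1-5% of one arm at a 50-60% event rate, the shift is about 0.2-1.5 points for the control arm (about 0.3-1.9 for the Synergy arm), well below the planned 7.75 points. It is zero if the withdrawn patients carry their arm's average risk. The correction is still warranted, because outcomes never collected may not be recoverable later. The phrases in sections 9.2 and 6.3 are wording to reconcile, not evidence of lost ITT data.

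**What to change.** - **Section 10.3:** state that every randomised patient stays in the ITT set and is followed on the scheduled visits from randomisation, whether or not PCI starts. Collection ends only when the patient withdraws consent to follow-up.
- **Section 13.2:** extend it to endpoint-related events in all randomised subjects, from randomisation.
- **Sections 10.3, 10.4 and 4-2:** reconcile them so that one rule covers a patient diverted before PCI starts, and so that section 4-2 gives a follow-up start for a patient with no baseline procedure.
- **Sections 9.2 and 6.3:** reconcile the other-BMS phrase with 10.4. Say how a patient randomised on valid verbal consent is handled if written consent is never obtained, within local law.

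The cost is protocol wording, an eCRF instruction and telephone follow-up of a few extra patients. Sample size and method of analysis are unchanged.

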10.4 Data Collection for patients who receive non-study stents

Patients who receive non-study stents or who undergo any non-study procedure for the treatment of coronary artery disease (i.e. any procedure that is not PCI with a study stent) for any reason, are considered major protocol violations and will be followed for the intent to treat (ITT) analysis only. Patient care (i.e. medical treatment, additional procedures) is left to the discretion of the investigator, however, patients must continue to be followed per protocol scheduled follow-up.

11- Study discontinuation rules

If the Sponsor, Data Safety and Monitoring Board, Regulatory Agency, and/or the Principal Investigator discover conditions during the study that indicate the investigation should be terminated for patient safety reasons, an appropriate schedule for termination will be setup.

12-Statistical design and analysis

The trial is designed to be a superiority trial. This is a randomized, controlled, single blind, multicentric, prospective trial. The primary endpoint is a composite of all-cause mortality, myocardial infarction, stroke or ischemia-driven TLR with an anticipated median follow-up of one year (**efficacy**).

The SENIOR study is powered to test the superiority of the EESbp with a relative 25% reduction in the active group.

Assuming the following:

- primary endpoint event rate is 31% in control treatment arm at 1 year (interpolated from the most contemporary and accurate reference)
- minimum time to follow-up is 1 year
- a constant dropout rate yielding 15% lost to follow-up at 1 year
- one-sided alpha = 0.025

then a sample size population of 560 subjects per arm will provide 80% power to demonstrate superiority using a chi-square test comparing the event rates at 1 year from the Kaplan-Meier curves. To take into account potential patients loss during follow up, the definitive total number will be **1,200 patients** (600 in each arm). The sample size calculation was performed in SAS version 9.2 using 10.000 simulations.

All statistical analyses will be described in a statistical analysis plan, which will be finalized before the end of the study.

13-Safety reporting

Safety of the subjects participating in this clinical trial will be monitored throughout the trial using the Adverse Event reporting process to identify real and potential safety issues.

Adverse events will be reported according to the ISO 14155:2011(E) Clinical Investigation of medical devices for human subjects – Good Clinical Practice Guidelines, while recognizing and following other specific laws, regulations, directives, standards and/or guidelines as appropriate as required by the country(ies) in which the study is conducted.

13.1 Definitions

13.1.1-Adverse Event (AE)

Any untoward medical occurrence, unintended disease or injury or untoward clinical signs (including an abnormal laboratory finding) in subjects, users or other persons whether or not related to the investigational medical device.

Note 1: This includes events related to the investigational medical device or the comparator.

Note 2: This includes events related to the procedures involved.

Note 3: For users or other persons this is restricted to events related to the investigational medical device.

Note 4: Pre-Existing Medical Conditions: Any medical conditions (including planned surgeries and planned hospitalizations) present at baseline, which do not worsen in duration, severity or frequency during the study are not adverse events (AE). These pre-existing medical conditions should be adequately documented in the patient's medical history. **Medical conditions present at baseline which worsen after exposure to study treatment will be recorded as an AE on the Adverse Event Form of the CRF.**

13.1.2-Adverse Device Effect (ADE)

Adverse event related to the use of an investigational medical device. This includes adverse events resulting from insufficient or inadequate instructions for use, deployment, implantation, installation, operation, or any malfunction of the investigational medical device. This also

includes any event resulting from the use error or intentional misuse of the investigational medical device.

13.1.3-Serious Adverse Event (SAE)

An adverse event that:

1. led to a death,
2. led to a serious deterioration in the health of the subject that either resulted in: 1) a life-threatening illness or injury, or 2) a permanent impairment of a body structure or a body function, or 3) in-patient or prolonged hospitalization, or 4) medical or surgical intervention to prevent life threatening illness or injury or permanent impairment to a body structure or a body function.
3. led to foetal distress, foetal death or a congenital abnormality or birth defect

Note: In accordance with Note 4 above: **A planned hospitalization for pre-existing condition, a planned surgery or a procedure required by the CIP without a serious deterioration in health is not considered to be an adverse event (serious or otherwise).**

13.1.4-Serious Adverse Device Effect (SADE)

Adverse device effect that has resulted in any of the consequences characteristic of a serious adverse event identified in the current version of the risk analysis report. Anticipated serious adverse device effect (ASADE) is an effect which by its nature, incidence, severity or outcome has been identified in the risk analysis report.

13.1.5- Unanticipated Serious Adverse Device Effect (USADE)

A serious adverse device effect which by its nature, incidence, severity or outcome has not been identified in the current version of the risk analysis report. Anticipated serious adverse

device effect (ASADE) is an effect which by its nature, incidence, severity or outcome has been identified in the risk analysis report.

13.1.6- Device Deficiencies (DD)

Inadequacy of a medical device with respect to its identity, quality, durability, reliability, safety or performance. Device deficiencies include malfunctions, use errors, and inadequate labeling.

Device deficiencies that did not lead to an adverse event but could have led to a medical occurrence:

1. if either suitable action had not been taken,
2. if intervention had not been made, or
3. if circumstances had been less fortunate

13.1.7- Device Malfunction

Failure of an investigational medical device to perform in accordance with its intended purpose when used in accordance with the instructions for use or CIP.

